#### **4.8.14. Telephone Visit (Visit 15, BP check; Study Day 59 + 2 Days)**

Subjects will complete a BP check approximately 3 days post last dose of study drug. On Study Day  $59 \pm 2$  days, subjects will participate in a telephone visit during which they will perform the following procedure at home:

- BP check

#### **4.8.15. Study Week 10 (Part 2 Only: Visit 16, End of Study; Study Day 70 $\pm 3$ Days)**

On Study Day  $70 \pm 3$  days, subjects will return to the site for an end-of-study visit scheduled 2 weeks after the last treatment with study drug and the following procedures will be performed:

- Vital signs (body temperature, heart rate, respiratory rate)
- AOBP (average of the last 2 of 5 unattended measurements using an automated oscillometric sphygmomanometer device after approximately 5 minutes of rest in the seated position)
- Blood draw ([Table 6](#))
  - Blood samples for aldosterone, cortisol, 11-deoxycorticosterone, 11-deoxycortisol, and PRA will be collected
  - Blood samples for hematology, chemistry, and coags will be collected, including hemoglobin A1c concentration and ACTH
- Urine will be collected for urinalysis ([Table 6](#))
- Review of AEs and concomitant medications

#### **4.8.16. Study Week 12 (Part 1 Only: Visit 16, End of Study; Study Day 84 $\pm 3$ Days)**

On Study Day  $84 \pm 3$  days, subjects will return to the site for an end-of-study visit scheduled 4 weeks after the last treatment with study drug and the following procedures will be performed:

- Vital signs (body temperature, heart rate, respiratory rate)
- AOBP (average of the last 2 of 5 unattended measurements using an automated oscillometric sphygmomanometer device after approximately 5 minutes of rest in the seated position)
- Blood draw ([Table 6](#))
  - Blood samples for aldosterone, cortisol, 11-deoxycorticosterone, 11-deoxycortisol, and PRA will be collected
  - Blood samples for hematology, chemistry, and coags will be collected, including hemoglobin A1c concentration and ACTH

- Urine will be collected for urinalysis ([Table 6](#))
- Review of AEs and concomitant medications

#### **4.9. Modifications to Study Conduct Due to the Coronavirus Disease 2019 (COVID-19) Pandemic**

As a consequence of the COVID-19 pandemic that has had a worldwide impact, control measures in place may impact the ability to adhere to some of the study procedures described in this protocol. Due to challenges that include, but are not limited to, subject COVID-19 infections, site closures, travel restrictions, and quarantines, some modifications to study conduct during the COVID-19 pandemic may be necessary to ensure study continuity, including conducting virtual visits when on-site study visits are considered not feasible. Such modifications in study conduct always must be in accordance with local regulations/mandates.

The following are allowable, as necessary, modifications to study conduct during the COVID-19 pandemic:

- Prior to a study visit at the site, the subject may be contacted and screened for potential exposure or infection to COVID-19 per site, local, or federal requirements. If the subject is suspected to be exposed or infected with COVID-19, the on-site visit should either be re-scheduled or a virtual visit may be performed instead, as applicable.
- In the event that a subject cannot attend their regularly scheduled study visits in person due to COVID-19 necessitating a limit on in-person contact, the investigator may perform safety and efficacy assessments by phone or video. The investigator may use the technology platform that is currently available to them. Virtual assessments may include home blood pressure evaluation initiated by the subject, adverse events, and concomitant medication review. Virtual assessments will be recorded by site staff in the source documents.
- Clinical laboratory tests (chemistry and hematology) and pregnancy tests may be performed by local laboratory, if sample collection cannot be performed at the study site due to COVID-19 related limitations, including but not limited to site closure. Abnormal laboratory results should be promptly communicated to the medical monitor. Subjects' anonymity must be maintained when communicating results to the medical monitor.
- At home IP administration may continue for up to 2 weeks (at multiple times during the study if required due to COVID-19, although not consecutively) if the subject has no relevant clinically significant out of range values per previous lab reports.
- Source documentation should note that the visit was performed virtually (not face-to-face) and note the name of the local lab where laboratory tests were done, if applicable.
- If certain study procedures or assessments cannot be completed per the schedule of events, the reason for the missed assessment (ie, laboratory tests, vital signs, physical examinations, etc) must be noted in the source documentation (eg, COVID-19), captured in the protocol deviations documentation, and reported to the IRB, as applicable.

A detailed assessment of COVID-19 related risk and mitigation measures will be documented in the appropriate study plans.

## 5. STUDY POPULATION

### 5.1. Inclusion Criteria

1. Male and nonpregnant, nonlactating female subjects  $\geq$  18 years of age. Fertile male and female subjects and their partners must agree to use either highly effective or acceptable methods of contraception as defined in [Appendix 12.8](#) from Screening to 90 days post last dose of study drug
2. Written informed consent Health Insurance Portability and Accountability Act authorization, and local patient privacy required documentation for this study have been obtained
3. Average of AOBP measurements taken at Screening/start of the Placebo Run-in Visit and Randomization with SBP  $\geq$  130 mmHg
4. Background antihypertensive treatment of  $\geq$  2 drugs (note: a combination pill = 2 antihypertensives) that have been stable at their prescribed doses for at least 4 weeks prior to signing the Screening/main study ICF
5. For Part 1, inclusion based on morning pre-Screening visit measurement of PRA, and the value for PRA must be  $\leq$  1 ng/mL/h. For Part 2, inclusion based on morning pre-Screening visit measurement of PRA, and the value of PRA must be  $>$  1 ng/mL/h. Alternative target PRA criteria for the study may be provided by the sponsor. These alternative targets may be adjusted during the conduct of the trial based on ongoing review of PRA values.
6. Inclusion based on morning pre-Screening visit measurement of serum aldosterone for Part 1 and pre-Screening visit measurement of aldosterone for Part 2. The value for aldosterone must be  $\geq$  1 ng/dL based on morning measurement. Alternative target aldosterone criteria for the study may be provided by the sponsor. These alternative targets may be adjusted during the conduct of the trial based on ongoing review of serum aldosterone values.
7. Serum cortisol  $\geq$  18 mcg/dL (morning measurement) or serum cortisol  $>$  3 and  $<$  18 mcg/dL (morning measurement) at Screening/start of Placebo Run-in visit if there is no evidence of adrenal insufficiency based on normal ACTH stimulation test results. In the event that ACTH stimulation testing cannot be performed due to logistical challenges, including supply chain limitations to availability of synthetic ACTH, then subjects may be entered into the trial if morning serum cortisol is  $>$  3 mcg/dL and they fulfill the criteria for no recent use of exogenous corticosteroid medications in dosages that could potentially cause adrenal suppression (ie, Exclusion Criteria 16a).
8. Women of childbearing potential must have a negative serum pregnancy test prior to Randomization
9. Willing and able to comply with the study instructions and attend all scheduled study visits

## 5.2. Exclusion Criteria

1. Concomitant use of epithelial sodium channel inhibitors or mineralocorticoid receptor antagonists, including, but not limited to amiloride, triamterene, spironolactone, eplerenone
2. Use of ACE inhibitors and ARBs in combination (ie, concomitant ACE inhibitors plus ARB therapy) as background antihypertensive treatment
3. Subjects with hypokalemia, ie, serum potassium < 3.0 mEq/L at Screening
4. Subjects with hyperkalemia, ie, serum potassium > 5.2 mEq/L at Screening for Part 1 and > 4.8 mEq/L at Screening for Part 2
5. Subjects with serum cortisol < 3 mcg/dL based on morning measurement at Screening
6. Subjects with serum sodium < 135 mEq/L at Screening
7. Subjects with estimated glomerular filtration rate < 60 mL/min/1.73m^2 at Screening
8. Subjects with type 1 or uncontrolled (hemoglobin A1c ≥ 9%) type 2 diabetes mellitus
9. Subjects with body mass index > 40 kg/m^2
10. Subjects with unstable angina who are taking short-acting oral or sublingual nitroglycerin or who have history of myocardial infarction or stroke within 6 months of Screening, sustained atrial fibrillation, ie, lasting > 12 months, or permanent atrial fibrillation; paroxysmal atrial fibrillation that terminates spontaneously or with intervention within 7 days is allowed. Chronic long-acting oral nitrates that have been stable at their prescribed doses for at least 2 weeks prior to signing the Screening/main study ICF are allowed.
11. Subjects with office SBP ≥ 175 mmHg or DBP ≥ 100 mmHg for Part 1 and SBP ≥ 160 mmHg or DBP ≥ 100 mmHg for Part 2 (average of last 2 of 5 unattended measurements using an automated oscillometric sphygmomanometer device after approximately 5 minutes of rest in the seated position) at Pre-Screening, Screening/Start of Placebo Run-in, or Randomization
12. Subjects with a decrease in SBP ≥ 20 mmHg or DBP ≥ 10 mmHg from sitting to standing position at Screening (may be repeated during Screening at the investigator's discretion)
13. Subjects who, in the opinion of the investigator, have suspected nonadherence to antihypertensive treatment
14. Subjects who, in the opinion of the investigator, have any major medical illness or symptoms of a clinically significant illness that may limit their ability to complete the study or influence subject safety and/or the study outcome (eg, active malignancy, HIV infection)
15. Subjects who, in the opinion of the investigator, have any acute or chronic medical or psychiatric condition or laboratory abnormality that would make them unsuitable for participation in this study or that would place the subject at undue risk (eg, history of

drug, alcohol, or other substance abuse) or who have other factors limiting the ability of the subject to cooperate and to comply with this protocol

16. Subjects undergoing treatment with any of the following medications:

- a. Chronically administered oral or topical corticosteroids within 3 months of Screening or during study participation. Short-term (ie,  $\leq$  2 weeks) of topical corticosteroids are allowed if taken  $\geq$  1 month prior to Randomization.
- b. Sympathomimetic decongestants within 1 week of Screening or during study participation
- c. Theophylline unless treatment has been stable at optimum dose for at least 4 weeks prior to Screening and remains stable during study participation
- d. Regular use of phosphodiesterase type 5 inhibitors within 3 months of Screening or during study participation
- e. Chronic use of nonsteroidal anti-inflammatory drugs (NSAIDs), other than low dose aspirin (81-325 mg), where chronic use is defined as  $>$  3 consecutive or nonconsecutive days of treatment per week, within 2 weeks of Screening. Note: intermittent use of NSAIDs is strongly discouraged; if required, NSAIDs must not be taken more than a total of 2 days during the study (defined as the period from Randomization to the end of study period). If analgesics are required, acetaminophen is recommended.
- f. Intramuscular steroids within 3 months of Screening or during study participation
- g. Estrogen- or progesterone-containing oral contraceptives or implantable progesterone devices
- h. Strong CYP3A and CYP3A4 inhibitors (eg, clarithromycin, telithromycin, nefazodone, itraconazole, ketoconazole, atazanavir, darunavir, indinavir, lopinavir, nelfinavir, ritonavir, saquinavir, tipranavir)
- i. Strong CYP3A and CYP3A4 inducers (eg, apalutamide, carbamazepine, enzalutamide, fosphenytoin, lumacaftor, mitotane, phenobarbital, phenytoin, primidone, rifampin, St. John's Wort)

17. Subjects with known hypersensitivity to MLS-101 or any of the excipients

18. Subjects who are night-shift workers

19. Subjects who are unable to comply with protocol requirements, including treatment compliance and instructions for ABPM

20. Subjects who are currently enrolled in an investigational drug or device study or have used an investigational drug or an investigational device treatment within 4 weeks of Screening (Note: Subjects who are enrolled in a long-term follow-up study and are not actively receiving an investigational drug or investigational device treatment may be eligible for participation in this study)

### **5.3. Lifestyle Considerations**

#### **5.3.1. Meals and Dietary Restrictions**

Dietary counseling reflecting the current standard of care will be provided to all subjects at each visit according to the instructions described in [Appendix 12.6](#).

#### **5.3.2. Caffeine, Alcohol, and Tobacco**

- Subjects will abstain from ingesting caffeine- or xanthine-containing products (eg, coffee, tea, cola drinks, and chocolate) for 30 minutes before the start of BP measurement and 12 hours before the start of dosing until after collection of the final PK (on Study Days 1, 7 ± 2, and 28 ± 2) and/or PD (at Pre-Screening, Screening/start of Placebo Run-in, and on Study Days 1, 28 ± 2, and 84 ± 3) sample.
- Subjects will abstain from alcohol for 30 minutes before the start of BP measurement and 24 hours before the start of dosing until after collection of the final PK (on Study Days 1, 7 ± 2, and 28 ± 2) and/or PD (at Pre-Screening, Screening/start of Placebo Run-in, and on Study Days 1, 28 ± 2, and 84 ± 3).
- Subjects who use tobacco products will be instructed that use of nicotine-containing products (including nicotine patches or gums and e-cigarettes) will not be permitted while they are in the clinical unit. Subjects will abstain from smoking for 30 minutes before the start of BP measurement.

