#### **4.8.13. Study Week 8 (Visit 14, Study Day 56 ± 2 Days)**

At the Study Week 8 visit (Visit 14), subjects will begin 24-hour ABPM procedure. On Study Day 56 ± 2 days, subjects will return to the site and the following procedures will be performed prior to site administration of the morning dose of study drug:

- Physical examination
- Vital signs (body temperature, heart rate, respiratory rate)
- AOBP (average of the last 2 of 5 unattended measurements using an automated oscillometric sphygmomanometer device after approximately 5 minutes of rest in the seated position)
- Standing BP assessment ([Appendix 12.5](#))
- Repeat 24-hour ABPM if procedure at Study Week 7 deemed a failure
- Spot urine collection (**Part 1 only**)
- Standard 12-lead ECG; ECG changes consistent with hyperkalemia will require confirmation of potassium levels at a local laboratory
- Pregnancy test (urine; women of childbearing potential only)
- Blood draw ([Table 6](#))

- Blood samples for hematology, chemistry, and coags will be collected, including hemoglobin A1c concentration, cortisol, and ACTH
- Single blood samples for determination of MLS-101 will be collected. Additional blood samples for long-term storage for metabolites, drug-drug interaction profiles of background therapy, or other exploratory analyses will also be collected.
- Blood samples for ACTH stimulation test ([Appendix 12.7](#))
- ACTH stimulation test (may be waived with sponsor's approval)
- Urine collection for urinalysis ([Table 6](#))
- Review of AEs, concomitant medications, and study drug compliance

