### 8.1. Efficacy Assessments

#### 8.1.1. Automated Office-Measured Blood Pressure

Accurate measurement of BP is essential to classify individuals and record study treatment effect; consequently, BP should be measured by an automatic BP device at the site that is identical for all participating sites and managed by qualified personnel. In addition, the same person should use the BP device for a given subject at each visit whenever possible, and the measurement should be performed using the same arm of the subject and the appropriate cuff size, as determined during the pre-Screening visit.

The BP must be measured at trough (ie, before study drug administration) and at approximately the same time of day (preferably between 7:00 and 10:00 am  $\pm 1$  hour). The subject should be relaxed, sitting in a chair (feet on floor, back supported) for  $> 5$  minutes. The subject should avoid caffeine, exercise, and smoking for at least 30 min before measurement, and ensure patient has emptied his/her bladder. Neither the subject nor the observer should talk during the rest period or during the measurement. Remove all clothing covering the location of cuff placement.

Details on BP procedure (measurement and transfer of data) including subject preparation (eg, arm selection, arm position, cuff size) will be provided in the BP manual and will follow the AHA guidelines.

At each timepoint indicated in the SoA, SBP and DBP will be measured 5 times using an automated oscillometric sphygmomanometer device provided by the sponsor after approximately 5 minutes of rest in the seated position according to the AHA Guidelines ([Muntner 2019](#)); the repeated measurements should be separated by 1 to 2 minutes. The last 2 of 5 unattended

measurements of SBP and DBP will be averaged for the analysis. In addition to sitting measurements, standing BP will be measured at Screening/start of Placebo Run-in, Randomization, Study Week 1, and Study Week 8 with the AOBP device to assess for hypotension according to the procedure provided in [Appendix 12.5](#).

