#### **8.4. Pharmacokinetics**

Single blood samples will be collected and tested for concentration of MLS-101 on Study Day 1 (predose) and at Study Weeks 1, 4, and 8 (trough levels). Additional blood samples for long-term storage for metabolites, drug-drug interaction profiles of background therapy, or other exploratory analyses will also be collected at baseline (predose) and at Study Weeks 1, 4, and 8. At selected sites, blood samples for determination of MLS-101 (and metabolites) will be collected predose, and 1, 2, 3, and 4 hours postdose on Study Days 1 (Randomization) and 28 (Study Week 4).

Instructions for collection, preparation, handling, and shipping PK specimens are provided in the Laboratory Manual for the study.

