#### **8.5. Pharmacodynamics**

Blood samples for aldosterone and PRA will be collected at Pre-Screening. Blood samples for aldosterone, cortisol, 11-deoxycorticosterone, 11-deoxycortisol, and PRA will be collected at Screening/start of Placebo Run-in, Study Day 1 (baseline), Study Week 4, and Study Week 10 for Part 2 or Study Week 12 for Part 1 (end of follow up).

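### The 12-hour caffeine and 24-hour alcohol restrictions in Protocol 5.3.2 omit Day 56 (Week 8 PK trough and primary-endpoint BP) and Day 70 (Part 2's final PD sample)

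*Protocol*

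**What the plan says.** Protocol 5.3.2 sets two layers of restriction. For caffeine, subjects abstain "for 30 minutes before the start of BP measurement and 12 hours before the start of dosing"; the alcohol bullet reads "Subjects will abstain from alcohol for 30 minutes before the start of BP measurement and 24 hours before the start of dosing". The 30-minute part attaches to every BP measurement. The longer part attaches to blood sampling. For PK it runs "until after collection of the final PK (on Study Days 1, 7 ± 2, and 28 ± 2"). A second list in the same bullets names the days for the other kind of sample: "PD (at Pre-Screening, Screening/start of Placebo Run-in, and on Study Days 1, 28 ± 2, and 84 ± 3").

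The sampling schedule is wider than those lists. Protocol 8.4 takes PK samples "on Study Day 1 (predose) and at Study Weeks 1, 4, and 8 (trough levels"), and the Week 8 visit procedures (Protocol 4.8.13) repeat it: "Single blood samples for determination of MLS-101 will be collected". Protocol 8.5 places the last PD sample at "Study Week 10 for Part 2 or Study Week 12 for Part 1 (end of follow up"). In Part 2 that visit is Day 70±3 (Protocol 4.8.15).

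For office BP, Protocol 8.1.1 says "The BP must be measured at trough (ie, before study drug administration") and asks for at least 30 minutes without caffeine. The primary endpoint is the change in office systolic BP from baseline to Week 8, Day 56±2 (Protocol 3.2.1).

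**The concern.** BP on visit days is taken before the morning dose. On a listed day, the abstention before dosing therefore covers the BP reading as well as the blood sample. Day 1 is listed and Day 56 is not. A subject who follows the protocol exactly has had no caffeine for 12 hours and no alcohol for 24 hours at the Day 1 reading, and may have had either up to 30 minutes before the Week 8 reading.

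The omission does not look deliberate. Week 8 has only a single trough sample, but so does Week 1, and Week 1 is listed. The amendment summary suggests how it arose: Amendment 1 added the Week 8 PK sample and Amendment 5 added the Part 2 Week 10 visit, while the current day list includes neither. That history is context only. The mismatch stands in the current text.

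At stake are outputs that compare one visit with another inside an arm, or one Part with the other, without a concurrent randomized control.

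**Working it through.** **Step 1. Set the 5.3.2 lists beside the schedule** (Protocol Tables 1 and 2, 4.8, 8.4, 8.5). Office BP is taken at every visit shown.

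| Visit | PK or PD sample | 12 h/24 h rule listed? |
|---|---|---|
| Pre-Screening, Screening | PD | Yes |
| Day −7 | none | No |
| Day 1 | PK and PD | Yes |
| Week 1 (Day 7) | PK trough | Yes |
| Weeks 2, 3 | none | No |
| Week 4 (Day 28) | PK and PD | Yes |
| Weeks 5, 6, 7 | none | No |
| **Week 8 (Day 56)** | **PK trough** | **No** |
| **Day 70 (Part 2)** | **PD** | **No** |
| Day 84 (Part 1) | PD | Yes |

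Every PK or PD visit is listed except Day 56 and Day 70.

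**Step 2. Which analyses are exposed.**

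- Dose versus placebo at Week 8 (SAP 6.4.1.2): the same rule applies in every arm, treatment is blinded, and SAP 5.3 analyzes each Part separately. Expected intake before the visit is the same in each randomized arm, so the difference is not biased.
- Within-arm change and each arm's ≤130/80 proportion (Protocol 9.3.2, SAP 6.4.2.4): no control is subtracted, so any effect of the looser conditions stays in the figure.
- The 100 mg contrast by PRA at Weeks 4 and 8 (SAP 6.4.1.3): in effect this sets Part 1 against Part 2, is not randomized and has no placebo adjustment. At Week 4 both Parts have the long rule. At Week 8 neither does, but Part 2 subjects should be fasted at all visits (Protocol 4.8) and Part 1 has no such rule for treatment visits. If fasting is taken to exclude morning coffee, conditions differ between the Parts.

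**Step 3. Precision.** The plan's own figure comes first. With SD 9 and 30 per arm (Protocol synopsis), the 90% half-width is 1.645 × 9 × √(2/30) = 3.82, matching the stated ±3.8.

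The documents give no figure for caffeine. For illustration only, *assume* that a proportion p of 0.3 to 0.5 take it between 12 hours and 30 minutes before the Week 8 reading, with a residual effect c of 3 to 8 mmHg. Assume also that the planning SD of 9 excludes this variation.

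*Baseline from Day 1 alone:*
- Shift in within-arm mean change = p × c: 0.3 × 3 = 0.9; 0.5 × 8 = 4.0 mmHg.
- SD = √(81 + p(1−p)c²): √(81 + 1.89) = 9.10; √(81 + 16) = 9.85.
- Half-width: 3.87 to 4.18.

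*Baseline as the mean of Day −7 and Day 1.* SAP 6.2.2 uses the last two non-missing predose values, which can be read this way. If the same subjects take caffeine on Day −7, where only the 30-minute rule applies, half the effect is already in the baseline:
- Shift = p × c / 2: 0.45 to 2.0 mmHg.
- SD = √(81 + p(1−p)c²/4): √81.47 = 9.03; √85 = 9.22.
- Half-width: 3.83 to 3.92.

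No range is offered for alcohol or for the PK trough, since the documents give no basis for one.

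**The case against.** The strongest reply is that the BP rule does not differ between visits. Protocol 5.3.2 and 8.1.1 apply the same 30-minute caffeine rule before every reading, and the longer rule belongs to PK and PD sampling. Day −7 and Weeks 2, 3, 5, 6 and 7 also have only the 30-minute rule, so Week 8 matches most on-treatment BP visits. This stands, and it means the defect is a day list that disagrees with the sampling schedule. It does not remove the by-product that Day 1 and Week 8 readings are taken under different conditions.

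The size is also open to attack: both caffeine inputs are assumed, and even the direction of the effect rests on knowledge from outside the documents. That stands too, so the figures above are an illustration and not an estimate.

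A reader might infer that the primary dose-versus-placebo result is biased. The documents do not support this, because the rule is common to all randomized arms. A reader might also infer that the Week 8 PK trough is compromised. Nothing in the documents says how caffeine or alcohol would alter it. The Part 1 versus Part 2 point is conditional, because no section defines whether fasting excludes coffee, and all Part 2 analyses are declared exploratory.

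Finally, a change to the text could hardly reach the Part 1 data. Amendment 6 is dated 07 July 2022, and SAP 2.5.2 dates the analysis at the end of Part 1 to July 2022. That is correct, and it is why the fix includes a reporting note.

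**Conclusion.** The point holds as a minor inconsistency. Day 56±2 and Day 70±3 are sampling days missing from the 5.3.2 lists, and this can be verified from the text alone. The consequence is limited to within-arm Week 8 change and the ≤130/80 rates, which are measured under conditions unlike Day 1, and possibly the non-randomized 100 mg contrast between Parts at Week 8.

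The placebo-adjusted difference is not biased, provided the comparison is made within each Part as SAP 5.3 plans. The precision effect is small: under the assumed inputs the half-width moves from 3.82 to at most 4.18, and to no more than 3.92 if baseline averages Day −7 and Day 1. The within-arm shift cannot be sized from the documents.

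**What to change.** In both the caffeine and the alcohol bullet of Protocol 5.3.2, add Day 56±2 to the PK days and Day 70±3 (Part 2) to the PD days, so that the lists agree with Protocol 8.4 and 8.5. For Week 8 visits already completed, state the difference in pre-measurement conditions when reporting within-arm results and the Part 1 versus Part 2 contrast.

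The cost is an edit to two bullets and a site reminder, with no new procedure. Subjects abstain before one more visit in Part 1 and two more in Part 2. The edit leaves Weeks 2, 3, 5, 6 and 7 under the 30-minute rule, so it aligns Week 8 with Day 1 but does not make conditions uniform across the weekly profile.
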